## 7.5 Efficacy Analyses

Summarization and analysis of efficacy parameters will be conducted for the ITT population (primary analysis) and PP population (secondary confirmatory analysis) by treatment group.

### 7.5.1 Primary Variable

The primary variable is the proportion of insulin-independent patients at Day 365 ± 14 days after IAT. The number and percentage of patients who are insulin-independent at Day 365 ± 14 days after IAT will be presented by treatment group overall and by IEQ/kg (<2500 IEQ/kg, 2500-5000 IEQ/kg, and >5000 IEQ/kg) infused at IAT.

The percentage of patients who are insulin-independent at Day 365 ± 14 days after IAT will also be presented graphically as a bar chart overall and by IEQ/kg group. Overall and within each IEQ/kg group there will be bars for reparixin and placebo.

#### Primary Analysis

The proportion of insulin-independent patients will be compared between treatment groups using the Cochran-Mantel-Haenszel test stratified by baseline IEQ/kg (<2500 IEQ/kg, 2500-5000 IEQ/kg, and >5000 IEQ/kg). The hypothesis to be tested is:

Null Hypothesis,  $H_0$ :  $p_{\text{reparixin}} \leq p_{\text{placebo}}$  for all baseline IEQ/kg strata

Alternative Hypothesis,  $H_A$ :  $p_{\text{reparixin}} > p_{\text{placebo}}$  for at least one baseline IEQ/kg strata

The significance level used for statistical testing will be 2.5% and a one-sided test will be used. The 95% confidence interval for treatment proportions and the one-sided 95% confidence interval for the difference in treatment proportion between reparixin and placebo will be produced.

As a sensitivity analysis, the primary analysis will be repeated for the ITT population, dropping from the analysis any site with >20% of subjects not having data for the primary endpoint recorded; subjects will be considered to not have data recorded for the primary endpoint if they have discontinued the study prior to attending the Day 365 visit or if they have attended the Day 365 visit but did not have the primary endpoint recorded. The intent is to examine the sensitivity of the primary analysis to sites lacking a reasonable number of patients with data captured for the primary endpoint.

The relevance of the treatment-by-site interaction will be investigated using a logistic regression model which will include the main effect of treatment and IEQ/kg infused at IAT (<2500 IEQ/kg,

REP0112

Statistical Analysis Plan

2500-5000 IEQ/kg, and >5000 IEQ/kg) and site as covariates. The analysis variable for treatment will be coded such that the reference treatment is placebo, the analysis variables for IEQ/kg infused at IAT will be coded such that the reference group is <2500 IEQ/kg, and the analysis variables for site will be coded such that the reference site is Site 1. The treatment-by-site interaction will be examined, and if not significant at the 0.10  $\alpha$ -level, will be removed from the model. The hypothesis to be examined is:

Null Hypothesis,  $H_0$ :  $\beta_{\text{treatment}} \leq 0$

Alternative Hypothesis,  $H_A$ :  $\beta_{\text{treatment}} > 0$

The treatment effect ( $\beta_{\text{treatment}}$ ) will be declared significantly greater than 0 at the 0.025  $\alpha$ -level. A model parameter estimate and the corresponding standard error, p-value, and odds ratio with a one-sided 95% confidence interval will be presented for the treatment effect.

The logistic regression sensitivity analysis will also be performed for the ITT population, dropping from the analysis any site with >20% of subjects not having the primary endpoint recorded, using the same approach used for the sensitivity analysis of the primary endpoint.

As further sensitivity analysis, the primary endpoint analysis and the corresponding logistic regression analysis will be repeated including Site 01 only, which is the largest site with the greatest number of patients receiving IAT, having possibly the best treatment balance, having a high rate of primary endpoint data capture, and also being the site with the highest experience in the field and thus transplanting patients under highly reproducible surgical and clinical conditions. When performing the logistic regression analysis, site will no longer be considered a covariate in the model. The intent of these analyses is to examine the sensitivity of the primary analysis to the low enrollment/treatment balance, lesser experience level, and lower rates of retention which may be present at the other sites.

For both the primary and sensitivity analyses, patients who die or who discontinue before the primary endpoint assessment at Day 365  $\pm$  14 days after IAT, or those who reach the Day 365 visit but have no primary endpoint assessment, will be treated as primary endpoint failures.

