## 6.2. DOSE, ROUTE AND SCHEDULE OF INVESTIGATIONAL PRODUCT ADMINISTRATION

Patients will receive either reparixin at a dose of 2.772 mg/kg body weight/hour for 7 days (168 hrs) or matched (flow rate/length of infusion) placebo, according to the randomization number.

The dosing solution (if reparixin, 11mg/mL) will be administered as a continuous i.v. infusion into a (high flow) central vein, by an infusion pump adequate to provide reliable infusion rates (see below), as per treatment schedule.

Infusion of the Investigational Product will start approximately 12hrs (allowed range 6-18hrs) before the anticipated time when islet infusion is started. The Investigator will identify the time to start study drug administration.

The pump rate will be adjusted to provide an infusion rate of approximately 0.25mL/kg/hour. Actual infusion rate (mL/hour), adjusted to body weight, is tabulated in [Appendix 14.3](#). Figures in the appendix represent mathematical rounding of original infusion rates derived from the following formula:

$$\text{Infusion rate (mL/hour)} = \frac{\text{dose (mg/kg/hour)} \times \text{body weight (kg)}}{11.00 \text{ mg/mL}}$$

Such a rounding affects actual administered dose/kg/hour by less than 1%.

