### 7.1. HOSPITAL STAY

#### 7.1.1. Screening and randomization

Potential study patients will be identified among those referring to the investigational site and found eligible as per site standard criteria for total (or completion) pancreatectomy followed by IAT. Consented patients will undergo the following screening evaluation, within 72 hours prior to randomization.

BP, HR, body weight (kg) and height (m) will be measured.

A baseline blood sample will be taken prior to any intervention for safety laboratory tests (assay as per centre practice). These include hematocrit, hemoglobin, red blood cells, platelets, white blood cells, differential white blood cells count, sodium, potassium, serum creatinine, blood urea nitrogen, total bilirubin, ALT, AST, INR, PTT. Albumin and pre-albumin will be also measured.

Pregnancy test (urine dipstick or blood test) will be performed, if appropriate.

Renal reserve will be assessed by CLcr (*Cockcroft-Gault*; 1976; see details in **Appendix 14.6.2**). Hepatic function will be assessed by ALT/AST and bilirubin.

Concurrent sepsis will be diagnosed by blood culture(s) and/or fever associated with other signs of systemic sepsis syndrome.

Pre-operative portal hypertension will be diagnosed as per clinical history **and** abdominal/liver imaging (e.g. presence/absence of varices, splenomegaly, Doppler waveforms and flow direction) by ultrasound techniques (e.g. duplex ultrasonography, spectral Doppler imaging and Color Doppler imaging, power Doppler imaging).

Two basal serum samples collected 6 to 24 hrs apart will be stored for centralized assay of pre-transplant chemokines/cytokines; similarly, a basal sample will be stored for centralized assay of pre-transplant miR-375 (see **Appendix 14.6.3**). All basal samples will be obtained before surgery and before Investigational Product administration is started.

Compliance with inclusion/exclusion criteria will be verified vs demographic, laboratory test results and clinical history/information available as per local standard clinical practice.

Eligible patients will be randomized (randomization number assigned) by an Investigator (or designee) before starting the infusion of the Investigational Product.

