### 7.1.3. Islet isolation and transplantation

Techniques for pancreas removal will be used, as per centre practice, including requirement for concomitant splenectomy.

Islet preparation: Site will process islets by enzymatic digestion using an FDA approved collagenase and neutral protease as per site specific standards. The pancreas will be distended by intraductal infusion of collagenase/neutral protease; if duct disruption prohibits intraductal infusion, enzyme will be manually injected into the pancreatic parenchyme. Pancreatic digestion will be performed using the semi-automated method of Ricordi. Purification will be performed when necessary to reduce tissue volume, dependent on site specific standards for islet manufacturing, using density centrifugation with COBE 2991. Samples will be taken from the pancreatic preservation solution and final islet product for sterility testing by gram stain and culture.

Islet mass will be assessed by manual counts as detailed in **Appendix 14.6.1** and quantified as total IEQ and IEQ/kg body weight. The final product is suspended in a 200 mL suspension of CMRL 1066 Transplant Media or equivalent solution. The final product is supplied in one to three 200 mL infusion bags, containing a minimum dose of >10,000 IEQ total.

Islet infusion: At all sites, islets will be transplanted on the same day as the total pancreatectomy procedure.

The islet mixture will be delivered slowly by gravity drainage into the portal vein or a tributary of the portal vein. Access to the portal vein may be obtained by direct cannulation during laparotomy or by percutaneous access by fluoroscopic, ultrasonographic, or real-time CT guidance.

At minimum, portal venous pressure will be monitored (direct venous measurement) before initiation, mid-way, and after completion of islet infusion. In case the portal pressure reaches >35 cmH2O, islet infusion will be put on hold, and restarted when portal pressure has dropped. In the rare event that portal pressure does not lower (within a 30 min interval), infusion is definitely stopped and any remaining tissue either discarded or placed in another tissue (e.g. peritoneal cavity, duodenal wall, underneath the kidney capsule, etc.).

The following isolation and operative details will be recorded in the CRF, as per documentations provided by the local Islet Processing Facility and centre information:

- Date and time of isolation (procedure completed);

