##### **9.4.2. Primary and Secondary Endpoint analysis**

For the primary efficacy endpoint, the proportion of insulin-independent patients over the time frame of day 365 $\pm$ 14 after the transplant, the differences in proportions will be assessed using the Pearson Chi-square statistic, stratified by the three groups at baseline: < 2500 IEQ/kg vs. 2500-5000 IEQ/kg vs. > 5000 IEQ/kg. The significance level used for statistical testing will be 2.5% and one-sided test will be used. The 95% confidence interval for treatment proportions and for the difference in treatment proportion between reparixin and placebo will be produced. The primary analysis will be performed using both ITT population with PP analysis serving as a sensitivity analysis.

For secondary endpoints that will be tested both at 75 $\pm$ 14 and 365 $\pm$ 14 days after the transplant, only the day 365 $\pm$ 14 time point will be tested for superiority in the fixed sequence testing procedure.

The C-peptide AUC after the MMTT normalized by IEQ/kg will be analyzed at the two time points by a repeated measurements model using PROC MIXED within SAS®, including terms for treatment, time point and center. The treatment effect within each time point will be compared using a two-sided test at the 5% level. The estimated treatment difference between reparixin and placebo at each time point will be presented together with the corresponding 95% confidence interval. The confidence interval will be generated using  $\alpha=0.05$ .

The mean in average daily insulin requirements at the two time points will be analyzed using a repeated measurements model using PROC MIXED within SAS®. The model will include fixed effect

terms for center, time point and treatment. Time point will be specified as a repeated measurement. The treatment effect within each time point will be compared using a two sided test at the 5% level.

The proportion of patients with an HbA1c  $\leq 6.5\%$  will be analyzed at day  $365 \pm 14$ . Additionally, the proportion of patients with an HbA1c  $\leq 6.5\%$  at day  $365 \pm 14$  will be analyzed again, but patients are included in this second analysis if they are also free of severe hypoglycemic events from day  $75 \pm 14$  to day  $365 \pm 14$  inclusive. Treatment effect will be analyzed using Pearson Chi-square.

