## 6 ANALYSIS POPULATIONS

Five analysis populations will be identified and used in the summarization and analysis of data, namely all screened patients, all randomized patients, intent to treat, per protocol, and safety.

- All Screened Patients: This population will include all patients screened for participation in the trial.
- All Randomized Patients: This population will include all patients randomized to investigational product in the trial.
- Intent to Treat: This population will consist of all patients who are randomized and receive the investigational product (either reparixin or placebo). Summarization and analysis of this population will be based on randomized treatment, regardless of treatment actually received. Eligible patients will be included in this population whether or not they receive IAT, because exclusions cannot be made for events occurring after randomization that could be influenced by the randomized assignment.
- Per Protocol: This population will consist of all patients in the ITT population who meet all of the following criteria:
  - Received IAT
  - Completed 7 days of investigational product dosing
  - No major protocol violations, including violations of inclusion/exclusion criteria, errors in treatment assignment, use of prohibited medication, etc.
  - Visits occurring on Day 75 ± 14 days from IAT and Day 365 ± 14 days from IAT
  - Insulin-independence status recorded at Day 365 ± 14 days from IAT

Further criteria for exclusion from the PP population may be identified during the data review meeting held prior to database lock.

- Safety: This population will consist of all randomized patients. Summarization and analysis of this population will be based on treatment actually received.

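### The primary test is stratified by a *baseline* IEQ/kg that is measured after randomisation and on study drug, and no readable planned test of the primary endpoint avoids conditioning on it

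*SAP*

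**What the plan says.** Protocol 9.4.2 has the primary comparison "stratified by the three groups at baseline: < 2500 IEQ/kg vs. 2500-5000 IEQ/kg vs. > 5000 IEQ/kg". SAP 7.5.1 makes this a CMH test, with the proportion insulin-independent "compared between treatment groups using the Cochran-Mantel-Haenszel test stratified by baseline IEQ/kg", and adds: "The significance level used for statistical testing will be 2.5% and a one-sided test will be used". Elsewhere in SAP 7.5.1, including the logistic model, the same categories are described as IEQ/kg infused at IAT.

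The order of events is set out in the protocol:

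- Section 7.1.1: "Eligible patients will be randomized (randomization number assigned) by an Investigator (or designee) before starting the infusion of the Investigational Product".
- Section 6.2: "Infusion of the Investigational Product will start approximately 12hrs (allowed range 6-18hrs) before the anticipated time when islet infusion is started".
- Section 7.1.3: after pancreatectomy and enzymatic isolation, "Islet mass will be assessed by manual counts as detailed in" Appendix 14.6.1. Infused IEQ/kg is recorded at transplant, and infusion can be stopped early for portal pressure.

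Some output not tested within IEQ/kg strata is already planned. SAP 7.5.1 gives the number and percentage insulin-independent by arm, both overall and within each IEQ/kg category. Protocol 9.1 and 9.4.2 and SAP 3.3 provide a 95% confidence interval for the difference, with no stratification mentioned. SAP 7.5.1 provides a one-sided 95% interval. The SAP addendum's insulin-requirement table shell prints N per IEQ/kg category and arm.

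**The concern.** A stratifier that treatment cannot affect only sharpens the comparison. One measured after treatment has begun may carry part of the treatment effect, and stratifying on it then removes that part. The stated objective (protocol 4.1, SAP 2) is the proportion insulin-independent after IAT, which includes anything the drug does to islet yield as well as to engraftment.

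The plan reasons this way when it defines ITT. SAP 6 keeps patients who never receive IAT because "exclusions cannot be made for events occurring after randomization that could be influenced by the randomized assignment". The primary test does not carry that caution over to IEQ/kg. It treats yield as unaffected by the drug without saying so, and plans no formal check. At stake is whether the primary p-value answers the stated question if yield turns out to differ between arms.

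**Working it through.** **1. Is IEQ/kg baseline?** The sequence is: randomise; start drug (6-18 h before islet infusion); pancreatectomy; isolation; count; infuse. No IEQ/kg exists before randomisation. Exposure before the count is somewhat shorter than 6-18 h, because the count precedes infusion and protocol 7.1.2 allows a halt of up to 6 h during surgery. It is exposure nonetheless.

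**2. Which tests condition on it?** The CMH test, its repeat without poorly captured sites, its Site 01 repeat, the logistic model with the same repeats, and the per-protocol versions (SAP 7.5, 7.5.1 and the table list in SAP 10). The unstratified Pearson wording in protocol 9.1 and SAP 3.3 belongs to the sample-size argument. The addendum's own section on the primary variable was not in the text available, so this statement covers the readable text only.

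**3. The plan's own figures.** For 23% v 55%, one-sided 0.025 and 90% power, the unpooled formula gives

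n = (1.960 + 1.282)² × (0.23×0.77 + 0.55×0.45) / 0.32² = 10.51 × 0.4246 / 0.1024 = 43.6, so 44 per arm, as stated.

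Exact Pearson power at 44 per arm is 88.8%, inside the stated 87-90%. CMH power at 50 per arm with half the patients in the middle stratum simulates at 89.9%. The sample size is not in question.

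**4. Overall rates implied by the documents** (strata 34/42/24%; control 13/23/55%; reparixin 40/55/84%):

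- Placebo: 0.34×0.13 + 0.42×0.23 + 0.24×0.55 = 27.3%
- Reparixin: 0.34×0.40 + 0.42×0.55 + 0.24×0.84 = 56.9%; difference 29.6 points

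**5. Assumed yield shifts.** The documents give no figure for a drug effect on yield, so these are scenarios. A lognormal with 34% below 2500 and 24% above 5000 has log-SD 0.693/(0.706 + 0.412) = 0.62. A 20% rise in yield then gives strata of 24/42/34%. The downward case is the mirror image, 44/42/14%.

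- Upward, no other effect: 0.24×0.13 + 0.42×0.23 + 0.34×0.55 = 31.5%; difference +4.2 points
- Downward, planned within-stratum effect: 0.44×0.40 + 0.42×0.55 + 0.14×0.84 = 52.5%; difference 25.2 points

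**6. Rejection rates**, simulated at 50 per arm, one-sided 0.025. CMH: Z = Σ(x_k − n_k m_k/N_k)/√ΣV_k, where in stratum k x_k and n_k are reparixin successes and patients, m_k and N_k are both-arm totals, and V_k is the hypergeometric variance. Unstratified: pooled two-proportion Z.

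| Scenario | Reparixin strata | True difference | CMH | Unstratified |
|---|---|---|---|---|
| No effect at all | 34/42/24 | 0 | 2.4% | 2.5% |
| Planned effect, yield unaffected | 34/42/24 | +29.6 | 89.6% | 86.8% |
| Yield up 10 points, nothing else | 24/42/34 | +4.2 | 2.5% | 6.6% |
| Everyone up one stratum, nothing else (extreme) | 0/34/66 | +16.8 | 2.6% | 41.8% |
| Planned effect, yield down 10 points | 44/42/14 | +25.2 | 89% | 75% |

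In the two yield-only rows both arms have the same success rate within every stratum, so CMH stays at its null rate however large the overall difference. The roughly 5 ITT patients expected not to receive IAT are left out.

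**7. Smooth model.** Three fixed rates overstate the removal, because yield gains inside a stratum also count. With the lognormal above and a logistic success curve fitted approximately to 13/23/55% (fitted 9.6/26.1/53.8%), a 20% higher yield gives +5.4 points overall and +0.9 points Mantel-Haenszel, so 83% is removed. Over yield rises of 10% to 50% the share removed is 83% to 81%.

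**The case against.** The case for leaving the plan alone has real force.

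- **No evidence of a yield effect.** Protocol 2.5 places the mechanism in inflammation around intra-portal infusion, that is, engraftment after the count. IEQ/kg is strongly prognostic on the protocol's own rates, and if yield is unaffected the CMH test holds its level and gains about 3 points of power. This stands, and is why the CMH test should be kept.
- **Much of the unconditioned result is already reported.** A two-sided 95% interval for the crude difference that excludes zero is close to the missing test. This stands in part. SAP 3.3 describes such an interval among its sample-size considerations. The interval in SAP 7.5.1 is one-sided 95%, so its bound does not match a one-sided 2.5% test, and the SAP does not say whether it is stratified. Nothing says how to read it beside the CMH result.
- **Imbalance would be visible.** A reader might infer that a shift in islet mass could pass unseen. The documents do not support that: category-level results by arm are planned. Only a formal comparison and a summary of IEQ/kg itself are absent.
- **The extra test is not powerful.** For the +4.2-point yield benefit it rejects in about 7% of trials. Its value is that it addresses the overall effect, not that it would rescue a small one.
- **The ITT principle concerns exclusions.** Stratifying is not excluding, so this is a parallel in reasoning, not a direct contradiction.

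**Conclusion.** The concern holds, conditionally. The label is wrong whatever the drug does: IEQ/kg is a post-randomisation, on-drug variable, and all readable primary-endpoint tests condition on it. The effect on the result depends on an unstated assumption that yield is unaffected. If that is true, the CMH test is valid and nothing is lost. If it is false, about 81-83% of the yield part of the effect is removed under the smooth model, and all of it under the three-rate model. The sizes of shift shown are assumptions, not estimates.

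Two stronger readings should be resisted. A reader might infer that the primary test is invalid; under the null with equal yield it rejects 2.4% of the time. A reader might also infer that it could declare benefit for a drug that is harmful overall. The scenarios worked here do not show that. Even with an assumed within-stratum odds ratio of 3 and 10- or 15-point downward shifts, the true difference still favours reparixin, by 17.2 and 14.8 points. CMH power there is about 65% and 64%, against 44% and 34% unstratified, so its significance is in the right direction. What it would not show is how much of the benefit had been offset.

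**What to change.** Keep the CMH test, its level and the sample size, and make four changes:

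1. In protocol 9.4.2 and SAP 7.5.1, replace baseline IEQ/kg with IEQ/kg infused (post-randomisation).
2. Add one ITT sensitivity test of the primary endpoint that does not condition on IEQ/kg, either unstratified or stratified by centre, which is fixed before randomisation. Report its two-sided 95% interval for the difference.
3. Add a by-arm summary and comparison of IEQ/kg infused and of the three category counts.
4. State in advance that if IEQ/kg differs between arms, the analysis not conditioned on it is read as the overall treatment effect.

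The cost is some wording and a small number of extra tables from data already collected (CRF page 12 holds infused IEQ/kg). The downside is one more sensitivity result to report and explain, about 3 points less powerful than CMH if yield is unaffected.
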